Prior to leaving, patients will be given a sufficient supply of study medication (or placebo) to last until the next in-clinic visit at Visit 3 along with instructions for their use. Patients should be instructed to take their medication every morning thereafter at or around the same time.

If a titration dose is missed, or if 4 or more consecutive daily doses are missed during treatment, restart at last dose taken.

Telephone visits at Day 7,21,35,49,63,84,140,196,252, and 308 (± 7 days)

Telephone visits will be used between dose increases to monitor any safety events with participants. In addition, telephone visits will serve as safety check-in.

The following procedures will be performed at all scheduled telephone visits as shown in the schedule of events:

- Medication reconciliation
- AE assessment

Visit 3 at Day 14 (± 7 days) 0.50mg/day

The following tests and procedures will be completed in clinic:

- Concomitant medication reconciliation
- Labs (CBC w/ diff, CMP, TSH)
- EKG (pre-dose, post-dose at 6-hours ± 10 minutes)
- Vital signs including weight (pre-dose)
- Vital signs (post-dose every hour ± 10 minutes for 6 hours)
- Neuro and physical exam
- Blood biomarkers
- Dispense study drug and drug diary
- Drug accountability
- Adverse event assessment

Visit 4 at Day 28 (± 7 days) 0.75mg/day

The following tests and procedures will be completed in clinic:

- Concomitant medication reconciliation
- Labs (CBC w/ diff, CMP, TSH)
- EKG (pre-dose, post-dose at 6-hours ± 10 minutes)
- Vital signs including weight (pre-dose)
- Vital signs (post-dose every hour ± 10 minutes for 6 hours)
- Neuro and physical exam
- Blood biomarkers
- Dispense study drug and drug diary in clinic
- Drug accountability
- Adverse event assessment

Visit 5 at Day 42 (± 7 days) 1 mg/day

The following tests and procedures will be completed in clinic:

- Concomitant medication reconciliation
- Labs (CBC w/ diff, CMP, TSH)
- EKG (pre-dose, post-dose at 6-hours ± 10 minutes)
- Vital signs including weight (pre-dose)

- Vital signs (post-dose every hour \pm 10 minutes for 6 hours)
- Neuro and physical exam
- Blood biomarkers
- Dispense study drug and drug diary in clinic
- Drug accountability
- Adverse event assessment

Visit 6 at Day 56 (\pm 7 days) 1 mg/day

The following tests and procedures will be completed in clinic:

- Concomitant medication reconciliation
- Labs (CBC w/ diff, CMP, TSH)
- EKG
- Vital signs including weight
- Neuro and physical exam

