- Dispense study drug and drug diary in clinic
- Drug accountability
- Adverse event assessment
- Blood biomarkers
- OCT Eye Exam

Visit 7 at Day 70 (\pm 7 days) 1mg/day

The following tests and procedures will be completed in clinic:

- Concomitant medication reconciliation
- Labs (CBC w/ diff, CMP, TSH)
- EKG
- Vital signs including weight
- Neuro and physical exam
- Blood biomarkers
- Dispense study drug and drug diary
- Drug accountability
- Adverse event assessment

Visit 8 at Day 112 (\pm 7 days) 1mg/day

The following tests and procedures will be completed in clinic:

- Concomitant medication reconciliation
- Labs (CBC w/ diff, CMP, TSH)
- EKG
- Vital signs including weight
- Neuro and physical exam
- Blood biomarkers
- Dispense study drug and drug diary
- Drug accountability
- Adverse event assessment

Visit 9 at Day 168 (\pm 7 days) 1mg/day

The following tests and procedures will be completed in clinic:

- Concomitant medication reconciliation
- Labs (CBC w/ diff, CMP, TSH)
- EKG
- OCT Eye exam
- Vital signs including weight

- Neuro and physical exam
- Blood biomarkers
- Cognitive assessments (MMSE, ADAS-Cog 13, CDR-SOB, ADCS-ADL)
- Dispense study drug and drug diary
- Drug accountability
- Volumetric MRI (+4 week window)
- Adverse event assessment

The following are to be completed if participants opted into one, or both, of the optional studies:

- *Saliva collection*

Visit 10 at Day 224 (\pm 7 days) 1mg/day

The following tests and procedures will be completed in clinic:

- Concomitant medication reconciliation
- Labs (CBC w/ diff, CMP, TSH)
- EKG
- Vital signs including weight
- Neuro and physical exam
- Blood biomarkers
- Dispense study drug and drug diary
- Drug accountability
- Adverse event assessment

Visit 11 at Day 280 (\pm 7 days) 1mg/day

The following tests and procedures will be completed in clinic:

- Concomitant medication reconciliation
- Labs (CBC w/ diff, CMP, TSH)
- EKG
- Vital signs including weight
- Neuro and physical exam
- Blood biomarkers
- Cognitive Assessments (MMSE, ADAS-Cog 13, CDR-SOB)
- Dispense study drug
- Drug accountability
- Adverse event assessment

*The following are to be completed if participants opted into one, or both, of the optional studies:
Saliva collection*

Visit 12 at Day 336 (\pm 7 days)

The following tests and procedures will be completed in clinic:

- Concomitant medication reconciliation
- Labs (CBC w/ diff, CMP, TSH)
- EKG
- Vital signs including weight
- Neuro and physical exam

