9. STUDY INTERVENTION DISCONTINUATION AND PARTICIPANT DISCONTINUATION/WITHDRAWAL

DISCONTINUATION OF STUDY INTERVENTION

A subject may discontinue study drug under any of the following circumstances:

- The subject wishes to discontinue study drug treatment for any reason.
- The subject experiences AEs that necessitate discontinuing study drug treatment. The Principal Investigator, medical monitor, and DSMB should be notified immediately.
- The investigator or DSMB decides to discontinue treatment for medical reasons. The reason for termination of study drug before study completion should be recorded in the CRF. At the time of study drug discontinuation, the End of Study Drug Visit should be administered. If the subject is not willing or able to return for all remaining study visits, they should be asked to return for the Week 52 and Week 78 visits, as well as returning all unused study drug. If this is not possible, they should be contacted by phone at Week 52 for the End of Study assessments (adverse events, and concomitant medications). The reason for withdrawal should be recorded in the case report form (CRF). The subject should complete the procedures for the Early Termination Visit, provided written consent to do so has not been withdrawn.

Subjects who discontinue or are withdrawn from the study following randomization:

- if they stop treatment (drug or placebo) before Visit 7, they will be replaced by new subjects
- if they stop treatment (drug or placebo) after Visit 7, they will not be replaced.

LOST TO FOLLOW-UP

To be considered lost to follow up, the study coordinator will make three documented attempts to contact the subject, who must also miss two scheduled visits. If these efforts are unsuccessful, a certified letter will be sent to the subject. If no response is received after this communication, then, the subject will be officially considered lost to follow up.

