The default Hotelling-Lawley F test is appropriate for this study, especially because it is the same as the Wald test in PROC MIXED with the DDFM=KR Kenward-Roger degrees-of-freedom method and an unstructured covariance model. We conjecture that the mean measure of brain atrophy will decrease by 20-30% (GLMPOWER Procedure SAS/STAT User's Guide 9.2). To characterize the variability, we specify a set of parameters that defines the entire covariance matrix of the residuals. We conjecture that the error standard deviation is the same at all four time points, with a value approximately 4-11, and we account for uncertainty by including both the lower and upper ends of this range in the sample size analysis. The power analysis is given in Table 1. A power of 90% is obtained with 90-95 subjects to determine a difference in brain atrophy over placebo. To account for a possible ~10% attrition rate, we will use 105 subjects in total.

Table 4: Power Analysis Versus Sample Size.

Index	Transformation	Effect	Actual Power	N Total
1	Time	Time	0.903	90
2	Mean (Dep)	Treatment	0.906	94

We chose to study mild AD subjects for the major reason that these patients do suffer continuous but limited/slow brain atrophy, which is measurable by vMRI²², vs. mild cognitive impairment patients (MCI), whose brain atrophy may not progress enough on an annual basis for robust quantification. Furthermore, the functional disabilities in mild AD patients are not too pronounced yet vs. moderate and severe AD. Thus, if Siponimod is able to slow down brain atrophy, mild AD subjects will likely benefit the most by, hopefully, also slowing down functional decline.

POPULATIONS FOR ANALYSES

All subjects receiving at least 1 dose of study drug will be included in the safety analyses. For efficacy analyses, subjects will be included only if they reach Visit 12 (Week 8) of the dosing period (i.e., patients withdrawn before Visit 12 and replaced will not be included in this efficacy analysis). Patients withdrawing or withdrawn from the study before Visit 12 are unlikely to demonstrate a change in the biomarkers investigated here (cognitive performance) given the effects of Siponimod in the CNS take several weeks to be measurable.

STATISTICAL ANALYSES

GENERAL APPROACH

All intra and inter-subject outcome measures collected during our study will be sent to [name] at Arizona State University for statistical processing.

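### The efficacy population is tied to Visit 12 (Week 8), but Visit 12 is Week 48 and Week 8 is Visit 6; every reading makes inclusion depend on retention after randomisation

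*Protocol*

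**What the plan says.** Section 12, Populations for Analyses, places every subject with at least one dose in the safety set but restricts efficacy: "For efficacy analyses, subjects will be included only if they reach Visit 12 (Week 8) of the dosing period". It then restates the rule: "patients withdrawn before Visit 12 and replaced will not be included in this efficacy analysis". The reason given is that "the effects of Siponimod in the CNS take several weeks to be measurable".

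Other parts of the protocol that bear on this rule:

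- Section 1.1 (Study Procedures) lists "Visit 12 at Day 336", "Visit 6 at Day 56" and "Visit 7 at Day 70". Table 1 in section 1.2 gives these visits as Weeks 48, 8 and 10.
- Section 9 on replacement: "if they stop treatment (drug or placebo) before Visit 7, they will be replaced by new subjects". Those who stop after Visit 7 are not replaced.
- Section 9 on follow-up: subjects who stop drug and cannot attend every remaining visit are still not released, because "they should be asked to return for the Week 52 and Week 78 visits".
- Section 10 (Procedure Used in Case of Toxicity): subjects taken off drug go directly to the End of Study Drug assessments, labelled Week 52 in Table 1, and then to the washout visits.
- Section 12, General Approach: missing data are not imputed, and rank-based methods are to bring in subjects who lack follow-up.

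**The concern.** There are two faults. First, the visit and the week in the rule do not match, and the restatement brings in a third cut-off. The mention of Week 8, the tie to replacement and the several-weeks rationale point to an early cut-off. The visit number, used three times in that paragraph, points to a late one. The difference matters most for a subject withdrawn between Visit 7 and Visit 12. Read by visit number, that subject is neither replaced nor analysed, even with a Week 24 vMRI on file. Read by the restatement, the same subject stays in. A toxicity withdrawal who goes straight to the End of Study Drug assessments never has a Visit 12. A subject who stops drug but keeps attending may or may not count as reaching it.

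Second, correcting the label does not cure the rule. Whichever week is meant, a randomised and dosed subject is dropped for something that happened after randomisation. The protocol itself expects drug-related withdrawals, so the arms compared need not be the arms randomised. If faster decliners stop siponimod more often than placebo, leaving them out favours siponimod with no drug effect. The vMRI comparison is the one the sample size was built on, and the same set governs the cognitive endpoints.

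**Working it through.** **1. Visit and week.** Study days come from section 1.1, checked against Table 1; week = day / 7.

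| Visit | Day | Week |
|---|---|---|
| 6 | 56 | 8 |
| 7 (end of replacement) | 70 | 10 |
| 9 (first post-baseline vMRI) | 168 | 24 |
| 12 | 336 | 48 |

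The stated pair, Visit 12 with Week 8, cannot be reproduced: 336 / 7 = 48, and 48 − 8 = 40 weeks. The ±7-day window does not bridge that gap.

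**2. The attrition figure.** The sample size text allows about 10% attrition. 94 / 0.9 = 104.4, which rounds up to the stated 105. The text does not give the period to which the 10% applies.

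**3. Head count excluded.** Assume 10% is lost over 52 weeks. With constant hazard, the number lost by week w is 105 × (1 − 0.9^(w/52)). With front-loading, half of the 10.5 stops (5.25) fall evenly in Weeks 0–10 and half evenly in Weeks 10–52.

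| Lost by | Constant hazard | Front-loaded |
|---|---|---|
| Week 8 | 1.7 | 4.2 |
| Week 10 | 2.1 | 5.2 |
| Week 24 | 5.0 | 7.0 |
| Week 48 | 9.7 | 10.0 |

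Of those lost by Week 48, 9.7 − 5.0 = 4.7 or 10.0 − 7.0 = 3.0 would have passed the Week 24 scan date. The scan window runs to +4 weeks, so slightly fewer may actually have been scanned. If the 10% is instead spread over all 78 weeks, constant hazard gives 1.1, 1.4 and 6.6 by Weeks 8, 10 and 48.

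**4. Size of the bias with no drug effect.** Assume decline has SD 1 and that stopping follows a latent normal variable with correlation ρ to decline. If a proportion p of an arm stops and is excluded, mean decline among those left falls by ρ·k(p), with k(p) = φ(z₁₋ₚ)/(1 − p). The spurious benefit is ρ·[k(p_siponimod) − k(p_placebo)]. Replacements pass through the same selection, so the formula also covers the early cut-off.

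| Stopping, siponimod vs placebo | k values | Difference | Bias at ρ = 0.3 to 0.5 |
|---|---|---|---|
| 12.5% vs 5% | 0.235, 0.109 | 0.127 | 0.04 to 0.06 SD |
| 6% vs 2% (early, with replacement) | 0.127, 0.049 | 0.077 | 0.02 to 0.04 SD |
| 30% vs 10% (stress) | 0.497, 0.195 | 0.302 | 0.09 to 0.15 SD |
| 10% vs 10% | 0.195, 0.195 | 0 | 0 |

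The first row matches planned attrition: (0.125 × 70 + 0.05 × 35)/105 = 10%. The stress row does not: (0.30 × 70 + 0.10 × 35)/105 = 23%.

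**5. Type I error.** Null trials of 70:35 were simulated, at least 20,000 per setting, with a two-sided 5% t-test in the included subjects. Across repeated runs the rates were about 5.3–6.3% (12.5% vs 5%), 4.8–5.7% (6% vs 2%), 6.7–11.0% (30% vs 10%) and 5% (equal stopping). With every stopper's outcome included, bias is 0 and the error rate about 5% in the differential cases. With half of them retrieved at 12.5% vs 5%, 0.02–0.03 SD of bias remains.

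**The case against.** The case for a lighter view has four parts.

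- **A wrong visit number is the simplest explanation.** Three clues point early and only the visit number points late. That is plausible, but the text does not prove it, and the visit number is repeated.
- **An early cut-off costs little.** The first scheduled post-baseline scan and cognitive tests are at Week 24, so a subject gone by Week 8 or 10 usually has no scheduled post-baseline efficacy data. This is largely right. The exceptions are the assessments at drug discontinuation and the Week 52 and 78 returns, which the rule would discard.
- **The bias is hypothetical.** The split between arms, the correlation and its direction are all assumed. The stated toxicity triggers are hepatic, haematological and cardiac, and nothing in the protocol links them to atrophy rate. With zero correlation there is no bias. The Week 48 figures also treat every subject who stops drug as excluded, which is the upper end because some may keep attending. In the early case the error rate is not clearly above 5%. All of this stands.
- **The stakes are limited.** The primary objective is safety, whose analysis set is sound, and only vMRI, not ADCOMS, was used for sizing. Some modelling detail could also sit in a separate analysis plan. These points stand too.

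None of them tells the reader which subjects are in the efficacy set. The definition is one the protocol itself states, so it was not left to a later document.

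**Conclusion.** The rule is wrong as written. Its visit and week differ by 40 weeks, neither matches the replacement cut-off, and no other text resolves the conflict. This part rests on the protocol's own schedule and is certain. It is also certain that every reading conditions efficacy inclusion on events after randomisation.

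The size of the bias is much less certain. At planned attrition it is small under the stated assumptions, and it vanishes if stopping is equal between arms or unrelated to decline. It becomes material only in the stress case, at more than twice the planned attrition. The need to correct the text therefore rests mainly on an efficacy population that cannot be determined, and on an exclusion that is avoidable. Leaving the cut-off open also allows it to be chosen once the pattern of dropout is known.

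**What to change.** - **Primary efficacy set:** all randomised subjects who took at least one dose, in their assigned arm, including those who stopped drug or were replaced.
- **Data and model:** use all available vMRI and cognitive assessments, placed by actual date, in a mixed model with unstructured covariance and Kenward-Roger degrees of freedom. The sample size text cites this model only to justify the power test, so it should be named as the analysis. It uses partial data without imputation.
- **Landmark set:** if one is kept, make it a sensitivity analysis with a single reconciled visit and week.
- **Rank-based methods:** state how that sentence in General Approach relates to the main analysis.
- **Timing after drug is stopped:** reconcile sections 9 and 10. Section 9 asks stoppers back at Weeks 52 and 78. Section 10 attaches the Week 52 assessments to the moment drug is withdrawn, so those scans may not fall at calendar Weeks 52 and 78.

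The cost is mostly wording, since return visits for stoppers are already planned, but the timing question has to be settled first. The statistical cost is some dilution from subjects off drug. If 12.5% of the siponimod arm stop and keep half the effect (assumed), the estimate shrinks by 0.125 × 0.5, or about 6%.

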severity³⁹. This inter-disciplinary teamwork resulted in a great interest to explore sphingosine-1-phosphate receptor (S1PR) modulators, particularly Siponimod, because they show both neuroprotective and immunomodulatory properties (see section C.). This collaboration led us to formulate the **central hypothesis that Siponimod could lower the rate of brain atrophy in AD subjects**.

To test our central hypothesis, we will carry out an 18-month Phase II, double-blind, randomized, two-armed, placebo controlled, proof-of-concept clinical study in early AD subjects (i.e. mild AD) who will be receiving an escalating dose of Siponimod or placebo in the ratio 2:1 for 12 months, followed by a 6-month washout period. The primary outcome measures are safety and tolerability of Siponimod in mild AD subjects. The secondary outcome measures are the rates of brain atrophy derived from volumetric MRI (vMRI) as a proxy for neurodegeneration conducted at baseline, 6, 12, and 18 months. The tertiary outcome measures are the changes in cognition and the levels of AD-associated (e.g., A β and tau) and inflammatory biomarkers in CSF after Siponimod exposure. In an exploratory effort, we will also measure plasma inflammatory markers during the entire duration of the study to investigate whether one or more of these markers can be used as dynamic surrogate markers of treatment response. Using our unique experience with the repurposing of immunomodulatory drugs for AD (and NCT #04032626), in the present project we are using elements of clinical trial design that we believe were successful and made some adjustments to fit the pharmacologic and toxic properties of Siponimod.⁸

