Dosing of Siponimod in AD is limited by two parameters. First, although no bradycardia was observed in a chronic high dose regimen in healthy subjects³⁸ and at therapeutic doses in MS patients undergoing a daily dose-titration regimen²⁷, these data were collected on young to middle-aged adults (age range 18-60). However, there is no literature on the possible cardiac AEs induced by Siponimod in older adults (age >60), which favors using a low dose in such individuals. Second, the *CYP2C9*2* and *CYP2C9*3* alleles are known to metabolize Siponimod more slowly than the *CYP2C9*1* genotype (half-lives of ~51 [double] and 126 hours [quintuple], respectively). *CYP2C9*2* allele is observed in 4-18% of Caucasians and Hispanics, which constitute a large proportion of the AD patients seen at BNI, and *CYP2C9*3* allele has a frequency of 2-20% in the same ethnicities, while Asians, African decedents, and Native Americans have lower frequencies for both genotypes^{33,43}. These observations of moderate frequencies for *CYP2C9*2* and *CYP2C9*3* alleles, and the recommendations from the FDA-approved package insert encourage us to administer the suggested low dose of 1 mg/day in *CYP2C9*1/x* and *CYP2C9*2/x* subjects, and to exclude *CYP2C9*3/3* subjects (0.4-0.5% of the population) for the present study. Consequently, and after discussing these issues with our MS specialty colleagues, for safety reasons we have selected to administer a maximum dose of 1 mg/day to the mild AD subjects that we will enroll in this proof-of-concept study. Further, instead of the daily titration regimen recommended in MS, we will apply a biweekly dose increment of 0.25 mg/day over the course of 6 weeks, with the first dose given at each increased strength (dose increases by 0.25 mg at a time) taken during in-person visits at BNI to monitor for any eventual AEs that could emerge with dose increases.

END OF STUDY DEFINITION

A participant is considered to have completed the study if he or she has completed all phases of the study including the last visit or the last scheduled procedure shown in the Schedule of Events (SOE).

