8. STUDY INTERVENTION

STUDY INTERVENTION(S) ADMINISTRATION

STUDY INTERVENTION DESCRIPTION

Siponimod is marketed by Novartis Pharmaceuticals Corporation under the name “Mayzent” registered under FDA IND #076122 (initially named “BAF-312”). The empirical formula is C₂₉H₃₅F₃N₂O₃, and the gram molecular weight is 516.6. Its chemical structure is shown below.

The formulation used in the present study will be provided by Novartis and is the same as indicated in IND #076122:

“Siponimod is provided as 0.25 mg film-coated tablets for oral use. Each film coated tablet contains 0.25 mg Siponimod, equivalent to 0.2 mg as Siponimod fumaric acid co-crystal. Siponimod film-coated tablets contain the following inactive ingredients: microcrystalline cellulose, crospovidone, glyceryl behenate, lactose monohydrate, colloidal silicon dioxide with a film coating containing lecithin (soy), iron oxides (red and black iron oxides for the 0.25mg), polyvinyl alcohol, talc, titanium dioxide, xanthan gum.”

Similarly, the placebo formulation will be provided by Novartis as explained in IND #076122: “The placebo tablets used in the studies described in this NDA have the same composition and configuration as the 0.25 mg drug products but do not contain Siponimod.”

DOSING AND ADMINISTRATION

The primary objectives of our project are the examination of drug safety and tolerability. This is an 18-month Phase II, double-blind, randomized, two-armed, placebo controlled, proof-of-concept clinical study. In total, we will enroll 105 early symptomatic AD subjects (i.e. mild AD) who will receive an escalating dose of Siponimod (0.25-1 mg/day) or placebo at a randomization ratio of 2:1 for 12 months (52 weeks), followed by a 6-month washout period (month 18). Study medications will be given orally, preferably in the morning. The patients and study staff will be blind to the randomization schema. For patients who meet all inclusion and exclusion criteria for enrollment, 35 will be randomly assigned to the placebo group, and 70 will be randomly assigned to the drug arm. There is no visual, taste, or smell difference between the placebo and Siponimod formulations. The randomization schedule will be developed by the study biostatistician.

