12. STATISTICAL CONSIDERATIONS

STATISTICAL HYPOTHESES

- Primary and Exploratory Efficacy Endpoint(s):

The null hypothesis for the primary efficacy endpoint is that biomarker measures (primary endpoint: vMRI; tertiary and exploratory endpoints: CSF biomarkers, blood inflammatory markers, saliva amyloid beta levels) will be the same in Siponimod- vs. placebo-treated study subjects after 12 months (end of dosing).

The alternative hypothesis is that Siponimod will improve biomarker measures at the same time point.

- Secondary Efficacy Endpoint(s):

The null hypothesis for the secondary efficacy endpoint is that cognitive measures (ADCOMS) will be the same in Siponimod - vs. placebo-treated study subjects after 12 (end of dosing) and 18 months (6 months follow up).

The alternative hypothesis is that Siponimod will improve cognitive measures at the same time points.

SAMPLE SIZE DETERMINATION

Mild AD subjects will receive an escalating dose of Siponimod up to 1 mg/day (N=70) or placebo (N=35) for 12 months (Table 2). We conducted a power analysis for sample size determination using the reported data from brain volume changes in SPMS subjects treated for at least 12 months with Siponimod or placebo²⁵. We wished to fit a repeated measures ANOVA model with two treatment levels in drug vs. placebo, and 4-time measures to receiving the drug (i.e. vMRI at baseline, 6, 12, and 18 months). We defined $Y_{ij} = \mu + \alpha_i + \tau_j + (\alpha\tau)_{ij} + \varepsilon_{ijk}$, where Y_{ijk} denotes the measure on brain atrophy, α_i denotes the treatment effect $i = 1, 2$; τ_j denotes the time effect at time $j=1, 2, 3, 4$; $k = 1, n$; $(\alpha\tau)_{ij}$ is the interaction between time and treatment; and ε_{ijk} is the error term²¹. We study the effect of the drug on brain atrophy. The between-subject factor in our model is treatment, with two levels (study drug and placebo), and we allocate each treatment in the ratio 2:1. The within-subject factor is time, with four levels (0, 6, 12, and 18 months). The number of patients needed is determined to achieve a power of 0.90 at significance level $\alpha = 0.05$ for the test of the interaction between time and treatment, where the contrast over time contains all pairwise comparisons. We also intend to generate a plot of power versus sample size that covers the power range of 0.05 to 0.90.

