The data will be summarized using professional standards. The distributions of patients completing each study visit and the reason for early terminations will be tabulated for each treatment group. The duration of double-blind treatment within each treatment group and compliance rates will be summarized by descriptive statistics (mean, standard error, standard deviation, median, minimum, maximum and sample size) for days of treatment and for total days of exposure and by the distributions of patients exposed to various durations of treatment categories. Demographic and baseline characteristics will be summarized by descriptive statistics for all patients in each treatment group.

Volumetric MRI data measures will be computed to determine eventual brain volume changes between pre- and post-treatment, which will validate or refute our central hypothesis. Data from Aims 2-3 will also be used in correlational analyses for blood vs. AD central markers to investigate whether minimally invasive tests that use peripheral markers could be used as proxies to track drug performance. We wish to fit a repeated measures ANOVA model with two treatment levels (drug and placebo) and 13 time measures (for blood markers). We define $Y_{ij} = \mu + \alpha_i + \tau_j + \varepsilon_{ijk}$, where Y_{ij} denotes the measure on siponimod, α_i denotes the treatment effect $i=1,2$, τ_j denotes the random effect at subject $j=1, 2, \dots, 70$, $k=1, \dots, 13$ and ε_{ijk} is the error term. We assume that the random effect is distributed with mean zero and σ^2 . Paired data tests will be used to assess eventual biomarker changes between pre- and post-dosing datasets. Correlational statistics and linear regressions will be employed to determine possible dose-response for siponimod on the biomarkers investigated. If siponimod has an effect on inflammatory and AD biomarkers (either in blood, or in CSF), the current study should demonstrate an amelioration of these biomarker profiles. Also, we will use the results of cognitive tests to calculate the average conversion rate, continuous variables, and time to event analysis in our two groups.

Missing data will not be imputed, and all summary statistics will be reported based upon observed data. For limited analyses where formal inferential analyses are specified, rank-based methods will be used to incorporate subjects missing follow-up assessments.

ANALYSIS OF THE PRIMARY EFFICACY ENDPOINT(S)

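### The blood-marker model has no visit or treatment-by-visit term and indexes only 70 subjects, so it cannot isolate the month-12 arm difference that the protocol hypothesises

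*Protocol*

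**What the plan says.** In protocol section 12, General Approach, the blood-marker analysis is introduced with "We wish to fit a repeated measures ANOVA model with two treatment levels (drug and placebo) and 13 time measures (for blood markers". The equation is an overall mean, a treatment effect, a tau term and an error. Tau "denotes the random effect at subject", with j running from 1 to 70, and the text adds "We assume that the random effect is distributed with mean zero". The index k runs from 1 to 13 and appears only on the error.

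The volumetric MRI model under Sample Size Determination differs. There tau is a time effect, and a further term "is the interaction between time and treatment".

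Under Statistical Hypotheses, blood inflammatory markers are among the biomarker measures that, under the null, "will be the same in Siponimod- vs. placebo-treated study subjects after 12 months (end of dosing".

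On numbers, section 8 states that "35 will be randomly assigned to the placebo group, and 70 will be randomly assigned to the drug arm". On timing, section 2.2 says "we will also measure plasma inflammatory markers during the entire duration of the study", which includes the six-month washout.

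Two other analyses bear on these markers. General Approach plans paired pre- and post-dosing tests. Exploratory Analyses plans comparisons of change from baseline but names no model.

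**The concern.** The hypothesis concerns one time point, the end of dosing, and compares two arms. The stated model has one treatment parameter, constant over time. It cannot give an arm difference at month 12, nor show whether the difference grows during titration or fades after stopping.

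If a marker responds on drug but not off it, the treatment term mixes full-dose visits with visits where the difference is smaller or nil, and the reported effect is too small. A null result could then come from averaging rather than from an inactive drug. Missing values are not to be imputed, so if the arms lose visits at different rates and the markers drift over time in both arms, a model without a visit term would also carry some of that drift into the treatment estimate.

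The subject index matters separately. A two-arm model indexed over 70 subjects does not describe this trial.

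**Working it through.** **1. Subjects.** 70 + 35 = 105. The index of 70 matches the drug arm alone.

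**2. Draws.** From the visit lists in section 1.1 and Table 1 in section 1.2:
- Baseline: 1
- Titration (Days 14, 28, 42): 3
- At 1 mg/day (Days 56, 70, 112, 168, 224, 280, 336, 364): 8
- Washout (Days 392, 546): 2

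The total is 1 + 3 + 8 + 2 = 14. The stated 13 is reproduced only by leaving one out; without baseline, 14 - 1 = 13.

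**3. What the treatment term estimates.** In a random-intercept model with complete data, the treatment contrast is the difference in subject means: (1/m) x sum of d_k, where d_k is the arm difference at draw k and m is the number of draws. With incomplete data it is a weighted average of the d_k.

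**4. Share of the full-dose difference recovered.** Assume d_k = 1 at the eight full-dose draws and 0 at baseline and in washout. For titration, section 6 says "we will apply a biweekly dose increment of 0.25 mg/day over the course of 6 weeks", so the draws at Days 14, 28 and 42 close the 0.25, 0.50 and 0.75 mg steps. The dose-proportional sum is 0.25 + 0.50 + 0.75 + 8 = 9.5.

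| Effect in titration | 13 post-baseline draws | All 14 draws |
|---|---|---|
| None | 8/13 = 0.615 | 8/14 = 0.571 |
| Proportional to dose | 9.5/13 = 0.731 | 9.5/14 = 0.679 |
| Full from Visit 3 | 11/13 = 0.846 | 11/14 = 0.786 |

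Whichever single draw is dropped to reach 13, the share stays between 7/13 = 0.54 and 11/13 = 0.85.

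**5. If the effect persists fully through washout.** Over 13 post-baseline draws the shares become 10/13 = 0.77, 11.5/13 = 0.88 and 13/13 = 1.00.

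**6. Is Week 56 off drug?** It falls 28 days after the end of dosing: 28 x 24 = 672 h. At the longest half-life quoted in section 6 (126 h), 672/126 = 5.3 half-lives, leaving about 2.5% of the drug. This concerns drug level; it does not show that the marker effect has gone.

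**7. Precision (illustrative).** Take single-draw SD 1, equal correlation rho of 0.3 to 0.9 between draws (assumed), 35 v 70 subjects and two-sided alpha 0.05. Set the effect so that the mean of the eight full-dose draws has 90% power: delta = (1.960 + 1.282) x sqrt(rho + (1 - rho)/8) x sqrt(1/35 + 1/70), which is 0.503 at rho = 0.5. The model's treatment term over 13 draws, dose-proportional case, then has about 66-70% power. A Week 52 contrast alone, without baseline adjustment, has 52% (rho = 0.3) to 87% (rho = 0.9). Week 52 is thus the right target but not always the more powerful test.

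**The case against.** The endpoint is exploratory, drives neither the sample size nor the safety objective, and the model is introduced tentatively. The notation is loose elsewhere in the section too. The index of 70 is most likely a slip, since the same text names two treatment levels; a reader might infer that the placebo arm is left out, and the text does not support that. All this limits severity. It does not remove the point, because the written definitions of the terms, not just the symbols, omit any time effect.

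A reader might also infer that pre-dose baseline is averaged into the treatment effect, that a chance imbalance there would count as drug effect, and that 13 is a miscount. The documents do not establish this. Exploratory Analyses speaks of change from baseline, and that turns 14 draws into 13 values. The text does not confirm this reading either, so the matter is open.

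A third inference would be that the plan cannot address its blood-marker objective at all. Section 4 frames that objective as before versus after treatment, and the paired tests and change-from-baseline comparisons bear on it. What stands is narrower: the paired tests are within-subject and give no drug-placebo contrast, and the change-from-baseline text names no model.

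Finally, the dilution figures rest on an assumed effect curve. That is correct, and bias toward zero should not be stated without that condition.

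**Conclusion.** The point holds in this form: the one between-arm model that the protocol writes out for blood markers cannot isolate the month-12 comparison that the protocol hypothesises for them, and its subject index does not fit the trial. Both follow from the text without assumptions. Because the protocol fixes the equation, this is not a detail left to a later analysis plan.

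The size is conditional. With a constant effect over the full-dose visits and none in washout, the treatment term recovers about 62-85% of the full-dose difference over 13 post-baseline draws, depending on the effect during titration, or 57-79% if baseline also enters. If the effect persists off drug, the loss is smaller and may vanish. Severity is low to moderate.

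**What to change.** Rewrite the blood-marker model in General Approach as follows.
- Index subjects over both arms, covering all randomised subjects in the stated analysis population. Reconcile this with Populations for Analyses, which limits efficacy analyses to those who reach Visit 12, so the number may be below 105.
- Add fixed visit and treatment-by-visit terms, with a random subject effect or another parsimonious covariance. An unstructured matrix is not suitable: 13 visits need 13 x 14/2 = 91 parameters and 14 need 14 x 15/2 = 105, for about 105 subjects.
- State whether baseline enters as a covariate or through change from baseline, and so reconcile 13 measures with 14 scheduled draws.
- Name the Week 52 treatment contrast as the test of the month-12 hypothesis, with washout visits kept out of that contrast. Given step 7, the average over the full-dose visits could be reported in support.

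The cost is a few sentences in the statistical section. No visit, sample or data item changes.
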